5.8. SAFETY ANALYSIS SET

The safety analysis (SAF) set will contain all patients in the RND set who receive at least one dose (or partial dose) of study medication and patients will be classified according to treatment received.

If there is any doubt whether a patient was treated or not, they will be assumed treated for the purposes of analysis. Sites number [REDACTED] will be excluded from this population.

5.9. EXTENDED SAFETY ANALYSIS SET

The Extended SAF set will contain all patients in the RND set who receive at least one dose (or partial dose) of study medication and patients will be classified according to treatment received.

If there is any doubt whether a patient was treated or not, they will be assumed treated for the purposes of analysis. Sites number [REDACTED] will be included in this population.

[REDACTED]

6. GENERAL CONSIDERATIONS

6.1. REFERENCE DATES AND STUDY DAY

Study Day will be calculated from the reference start date and will be used to show start/stop day of assessments and events.

Reference start date is defined as the day of the first dose of study medication (Day 1 is the day of the first dose of study medication) and will appear in every listing where an assessment date or event date appears.

- If the date of the event is on or after the reference start date, then:
Study Day = (date of event – reference start date) + 1.
- If the date of the event is prior to the reference start date, then:
Study Day = (date of event – reference start date).

In the situation where the event date is partial or missing, the date will appear partial or missing in the listings, and Study Day, and any corresponding durations will be presented based on the imputations specified in Appendix 2 of the SAP.

Reference end date is defined as the date of the last dose of study medication.

6.2. BASELINE

Unless otherwise specified, baseline is defined as the last non-missing measurement taken prior to reference start date (including unscheduled assessments). In the case where the last non-missing measurement and the reference start date coincide, that measurement will be considered baseline, unless time is present. If time of the assessment is on or after the study treatment start date, then the assessment is not considered baseline except in the following case: for main and responder SGRQ analysis, if the assessment on the day of randomization is done after dosing but prior to leaving the clinic after the 4 hour spirometry, the assessment is considered baseline. Adverse Events (AEs) and medications commencing on the reference start date will be considered post-baseline, ECG abnormalities from pre-dose assessments and laboratory abnormalities from pre-dose draws that are analyzed externally post-dose are still considered baseline.

Baseline for the spirometry endpoints is defined as the mean of the 2 measurements taken pre-dose on Day 1 prior to reference start date and time, unless only 1 measurement is taken pre-dose on Day 1 prior to reference start date and time.

[REDACTED]

If the baseline visit is split across in 2 days with pre-dose assessments on Day -1 and dosing on Day 1, then measurement from day – 1 will constitute baseline for spirometry endpoints.

6.3. RETESTS, UNSCHEDULED VISITS AND EARLY TERMINATION DATA

In general, for by-visit summaries, data recorded at the nominal visit will be presented.

Patients who were a screen failure and received approval from the Medical Monitor for rescreening will go through all of the original screening assessments. Data from the latest rescreened visit will be used in the summaries, however all screening information will be listed. Rescreened patients will keep the same patient number, as for the initial screening.

Unscheduled measurements will not be included in by-visit summaries but will contribute to the EOS value, or best/ worst case value where required (e.g. shift table).

Early termination data will be mapped to the next available visit number for by-visit summaries, as described in Section 6.4 of the SAP.

Post-randomization if ECG result is Abnormal, Clinically Significant, then triplicate ECGs should be provided.

Listings will include scheduled, unscheduled, retest and early discontinuation data.

6.4. WINDOWING CONVENTIONS

Each visit (except for Day 1 visit) will have a ± 10 days window. No visit windowing will be applied during the analysis to the data that is only collected at scheduled site visits for patients that have completed the study, and therefore the data will be presented as per the visit reported in the database.

For endpoints based on 12 hour spirometry data, (FEV1 AUC0-12h, FEV1 evening trough and FEV1AUC6-12h), data collected at visits with 12 hour spirometries will be included in the analysis regardless of the timepoint it was generated. Hence, no windowing convention applied to these endpoints.

For the patients that discontinued from the study, the End of Study (EOS) visit will be windowed to the corresponding visit, based on the study day, for questionnaire, spirometry and rescue medication data. The EOS visit can only be windowed to a visit that is missing or has a missing result. The rules for the windowing are described below.

[REDACTED]	[REDACTED]	[REDACTED]	[REDACTED]
[REDACTED]	[REDACTED]	[REDACTED]	[REDACTED]
[REDACTED]	[REDACTED]	[REDACTED]	[REDACTED]
[REDACTED]	[REDACTED]	[REDACTED]	[REDACTED]

- For spirometry raw data and derived data that happens at every visit, windowing will be done as per the corresponding visits.
 - Day 1 = Day 1
 - Week 6 = after Day 1 and up to and including Day 53
 - Week 12 = after Day 53 and up to and including Day 95
 - Week 24= after Day 95 and up to and including Day 179
- For spirometry derived data that only happen at certain visits, windowing will be done for the corresponding visits.
 - For morning trough:
 - Week 6 = after Day 1 and up to and including Day 53
 - Week 12 = after Day 53 and up to and including Day 95
 - Week 24= after Day 95 and up to and including Day 179
 -
- For rescue medication data, E-RS/EXACT-PRO, e-diary data and COPD exacerbation, windowing will be done as per the corresponding visits. Specifically, rescue medication data, E-RS/EXACT-PRO, e-diary data windowing conventions will be up to Week 24 whilst COPD exacerbation will be up to Week 48.
- - For patients who completed the study or who discontinue study medication but continue in the study:
- Week 24 subset:
 - Week 1 = Actual study Day of Week 24 visit minus 168 days (inclusive) up to and including actual study day of week 24 visit minus 161 days
 - Week 2 = Actual study Day of Week 24 visit minus 161 days up to and including actual study day of week 24 visit minus 154 days
 - Week 3 = Actual study Day of Week 24 visit minus 154 days up to and including actual study day of week 24 visit minus 147 days
 - Week 4 = Actual study Day of Week 24 visit minus 147 days up to and including actual study day of week 24 visit minus 140 days
 - Week 5 = Actual study Day of Week 24 visit minus 140 days up to and including actual study day of week 24 visit minus 133 days
 - Week 6 = Actual study Day of Week 24 visit minus 133 days up to and including actual study day of week 24 visit minus 126 days
 - Week 7 = Actual study Day of Week 24 visit minus 126 days up to and including actual study day of week 24 visit minus 119 days
 - Week 8 = Actual study Day of Week 24 visit minus 119 days up to and including actual study day of week 24 visit minus 112 days
 - Week 9 = Actual study Day of Week 24 visit minus 112 days up to and

- including actual study day of week 24 visit minus 105 days
- Week 10 = Actual study Day of Week 24 visit minus 105 days up to and including actual study day of week 24 visit minus 98 days
- Week 11 = Actual study Day of Week 24 visit minus 98 days up to and including actual study day of week 24 visit minus 91 days
- Week 12 = Actual study Day of Week 24 visit minus 91 days up to and including actual study day of week 24 visit minus 84 days
- Week 13 = Actual study Day of Week 24 visit minus 84 days up to and including actual study day of week 24 visit minus 77 days
- Week 14 = Actual study Day of Week 24 visit minus 77 days up to and including actual study day of week 24 visit minus 70 days
- Week 15 = Actual study Day of Week 24 visit minus 70 days up to and including actual study day of week 24 visit minus 63 days
- Week 16 = Actual study Day of Week 24 visit minus 63 days up to and including actual study day of week 24 visit minus 56 days
- Week 17 = Actual study Day of Week 24 visit minus 56 days up to and including actual study day of week 24 visit minus 49 days
- Week 18 = Actual study Day of Week 24 visit minus 49 days up to and including actual study day of week 24 visit minus 42 days
- Week 19 = Actual study Day of Week 24 visit minus 42 days up to and including actual study day of week 24 visit minus 35 days
- Week 20 = Actual study Day of Week 24 visit minus 35 days up to and including actual study day of week 24 visit minus 28 days
- Week 21 = Actual study Day of Week 24 visit minus 28 days up to and including actual study day of week 24 visit minus 21 days
- Week 22 = Actual study Day of Week 24 visit minus 21 days up to and including actual study day of week 24 visit minus 14 days
- Week 23 = Actual study Day of Week 24 visit minus 14 days up to and including actual study day of week 24 visit minus 7 days
- Week 24 = Actual study Day of Week 24 visit minus 7 days up to and including actual study day of week 24 visit
-
- Week 48 subset:
- Week 1 = Actual study Day of Week 48 visit minus 336 days (inclusive) up to and including actual study day of week 48 visit minus 329 days
- Week 2 = Actual study Day of Week 48 visit minus 329 days up to and including actual study day of week 48 visit minus 322 days
- Week 3 = Actual study Day of Week 48 visit minus 322 days up to and including actual study day of week 48 visit minus 315 days

[REDACTED]

- Week 4 = Actual study Day of Week 48 visit minus 315 days up to and including actual study day of week 48 visit minus 308 days
- Week 5 = Actual study Day of Week 48 visit minus 308 days up to and including actual study day of week 48 visit minus 301 days
- Week 6 = Actual study Day of Week 48 visit minus 301 days up to and including actual study day of week 48 visit minus 294 days
- Week 7 = Actual study Day of Week 48 visit minus 294 days up to and including actual study day of week 48 visit minus 287 days
- Week 8 = Actual study Day of Week 48 visit minus 287 days up to and including actual study day of week 48 visit minus 280 days
- Week 9 = Actual study Day of Week 48 visit minus 280 days up to and including actual study day of week 48 visit minus 273 days
- Week 10 = Actual study Day of Week 48 visit minus 273 days up to and including actual study day of week 48 visit minus 266 days
- Week 11 = Actual study Day of Week 48 visit minus 266 days up to and including actual study day of week 48 visit minus 259 days
- Week 12 = Actual study Day of Week 48 visit minus 259 days up to and including actual study day of week 48 visit minus 252 days
- Week 13 = Actual study Day of Week 48 visit minus 252 days up to and including actual study day of week 48 visit minus 245 days
- Week 14 = Actual study Day of Week 48 visit minus 245 days up to and including actual study day of week 48 visit minus 238 days
- Week 15 = Actual study Day of Week 48 visit minus 238 days up to and including actual study day of week 48 visit minus 231 days
- Week 16 = Actual study Day of Week 48 visit minus 231 days up to and including actual study day of week 48 visit minus 224 days
- Week 17 = Actual study Day of Week 48 visit minus 224 days up to and including actual study day of week 48 visit minus 217 days
- Week 18 = Actual study Day of Week 48 visit minus 217 days up to and including actual study day of week 48 visit minus 210 days
- Week 19 = Actual study Day of Week 48 visit minus 210 days up to and including actual study day of week 48 visit minus 203 days
- Week 20 = Actual study Day of Week 48 visit minus 203 days up to and including actual study day of week 48 visit minus 196 days
- Week 21 = Actual study Day of Week 48 visit minus 196 days up to and including actual study day of week 48 visit minus 189 days
- Week 22 = Actual study Day of Week 48 visit minus 189 days up to and including actual study day of week 48 visit minus 182 days
- Week 23 = Actual study Day of Week 48 visit minus 182 days up to and

[REDACTED]

- including actual study day of week 48 visit minus 175 days
- Week 24 = Actual study Day of Week 48 visit minus 175 days up to and including actual study day of week 48 visit minus 168 days
- Week 25 = Actual study Day of Week 48 visit minus 168 days up to and including actual study day of week 48 visit minus 161 days
- Week 26 = Actual study Day of Week 48 visit minus 161 days up to and including actual study day of week 48 visit minus 154 days
- Week 27 = Actual study Day of Week 48 visit minus 154 days up to and including actual study day of week 48 visit minus 147 days
- Week 28 = Actual study Day of Week 48 visit minus 147 days up to and including actual study day of week 48 visit minus 140 days
- Week 29 = Actual study Day of Week 48 visit minus 140 days up to and including actual study day of week 48 visit minus 133 days
- Week 30 = Actual study Day of Week 48 visit minus 133 days up to and including actual study day of week 48 visit minus 126 days
- Week 31 = Actual study Day of Week 48 visit minus 126 days up to and including actual study day of week 48 visit minus 119 days
- Week 32 = Actual study Day of Week 48 visit minus 119 days up to and including actual study day of week 48 visit minus 112 days
- Week 33 = Actual study Day of Week 48 visit minus 112 days up to and including actual study day of week 48 visit minus 105 days
- Week 34 = Actual study Day of Week 48 visit minus 105 days up to and including actual study day of week 48 visit minus 98 days
- Week 35 = Actual study Day of Week 48 visit minus 98 days up to and including actual study day of week 48 visit minus 91 days
- Week 36 = Actual study Day of Week 48 visit minus 91 days up to and including actual study day of week 48 visit minus 84 days
- Week 37 = Actual study Day of Week 48 visit minus 84 days up to and including actual study day of week 48 visit minus 77 days
- Week 38 = Actual study Day of Week 48 visit minus 77 days up to and including actual study day of week 48 visit minus 70 days
- Week 39 = Actual study Day of Week 48 visit minus 70 days up to and including actual study day of week 48 visit minus 63 days
- Week 40 = Actual study Day of Week 48 visit minus 63 days up to and including actual study day of week 48 visit minus 56 days
- Week 41 = Actual study Day of Week 48 visit minus 56 days up to and including actual study day of week 48 visit minus 49 days
- Week 42 = Actual study Day of Week 48 visit minus 49 days up to and including actual study day of week 48 visit minus 42 days

[REDACTED]

[REDACTED]

[REDACTED]

[REDACTED]

[REDACTED]

- Week 43 = Actual study Day of Week 48 visit minus 42 days up to and including actual study day of week 48 visit minus 35 days
- Week 44 = Actual study Day of Week 48 visit minus 35 days up to and including actual study day of week 48 visit minus 28 days
- Week 45 = Actual study Day of Week 48 visit minus 28 days up to and including actual study day of week 48 visit minus 21 days
- Week 46 = Actual study Day of Week 48 visit minus 21 days up to and including actual study day of week 48 visit minus 14 days
- Week 47 = Actual study Day of Week 48 visit minus 14 days up to and including actual study day of week 48 visit minus 7 days
- Week 48 = Actual study Day of Week 48 visit minus 7 days up to and including actual study day of week 48 visit
-
- For patients who discontinue the study before Week 24 (for 24-week stratum) or Week 48 (for 48-week stratum):
 - Week 24 subset:
 - Week 1 = on or after Day 1 and up to and including Day 8
 - Week 2 = after Day 8 and up to and including Day 15
 - Week 3 = after Day 15 and up to and including Day 22
 - Week 4 = after Day 22 and up to and including Day 29
 - Week 5 = after Day 29 and up to and including Day 36
 - Week 6 = after Day 36 and up to and including Day 43
 - Week 7 = after Day 43 and up to and including Day 50
 - Week 8 = after Day 50 and up to and including Day 57
 - Week 9 = after Day 57 and up to and including Day 64
 - Week 10 = after Day 64 and up to and including Day 71
 - Week 11 = after Day 71 and up to and including Day 78
 - Week 12 = after Day 78 and up to and including Day 85
 - Week 13 = after Day 85 and up to and including Day 92
 - Week 14 = after Day 92 and up to and including Day 99
 - Week 15 = after Day 99 and up to and including Day 106
 - Week 16 = after Day 106 and up to and including Day 113
 - Week 17 = after Day 113 and up to and including Day 120
 - Week 18 = after Day 120 and up to and including Day 127
 - Week 19 = after Day 127 and up to and including Day 134
 - Week 20 = after Day 134 and up to and including Day 141
 - Week 21 = after Day 141 and up to and including Day 148
 - Week 22 = after Day 148 and up to and including Day 155
 - Week 23 = after Day 155 and up to and including Day 162

[REDACTED]

- Week 24 = after Day 162 and up to and including Day 169
-
- Week 48 subset:
 - Week 1 = on or after Day 1 and up to and including Day 8
 - Week 2 = after Day 8 and up to and including Day 15
 - Week 3 = after Day 15 and up to and including Day 22
 - Week 4 = after Day 22 and up to and including Day 29
 - Week 5 = after Day 29 and up to and including Day 36
 - Week 6 = after Day 36 and up to and including Day 43
 - Week 7 = after Day 43 and up to and including Day 50
 - Week 8 = after Day 50 and up to and including Day 57
 - Week 9 = after Day 57 and up to and including Day 64
 - Week 10 = after Day 64 and up to and including Day 71
 - Week 11 = after Day 71 and up to and including Day 78
 - Week 12 = after Day 78 and up to and including Day 85
 - Week 13 = after Day 85 and up to and including Day 92
 - Week 14 = after Day 92 and up to and including Day 99
 - Week 15 = after Day 99 and up to and including Day 106
 - Week 16 = after Day 106 and up to and including Day 113
 - Week 17 = after Day 113 and up to and including Day 120
 - Week 18 = after Day 120 and up to and including Day 127
 - Week 19 = after Day 127 and up to and including Day 134
 - Week 20 = after Day 134 and up to and including Day 141
 - Week 21 = after Day 141 and up to and including Day 148
 - Week 22 = after Day 148 and up to and including Day 155
 - Week 23 = after Day 155 and up to and including Day 162
 - Week 24 = after Day 162 and up to and including Day 169
 - Week 25 = after Day 169 and up to and including Day 176
 - Week 26 = after Day 176 and up to and including Day 183
 - Week 27 = after Day 183 and up to and including Day 190
 - Week 28 = after Day 190 and up to and including Day 197
 - Week 29 = after Day 197 and up to and including Day 204
 - Week 30 = after Day 204 and up to and including Day 211
 - Week 31 = after Day 211 and up to and including Day 218
 - Week 32 = after Day 218 and up to and including Day 225
 - Week 33 = after Day 225 and up to and including Day 232
 - Week 34 = after Day 232 and up to and including Day 239
 - Week 35 = after Day 239 and up to and including Day 246
 - Week 36 = after Day 246 and up to and including Day 253

[REDACTED]

- Week 37 = after Day 253 and up to and including Day 260
- Week 38 = after Day 260 and up to and including Day 267
- Week 39 = after Day 267 and up to and including Day 274
- Week 40 = after Day 274 and up to and including Day 281
- Week 41 = after Day 281 and up to and including Day 288
- Week 42 = after Day 288 and up to and including Day 295
- Week 43 = after Day 295 and up to and including Day 302
- Week 44 = after Day 302 and up to and including Day 309
- Week 45 = after Day 309 and up to and including Day 316
- Week 46 = after Day 316 and up to and including Day 323
- Week 47 = after Day 323 and up to and including Day 330
- Week 48 = after Day 330 and up to and including Day 337

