9.2 Sample Size Determination

Approximately 800 patients will be randomized. The standard deviation for the change in FEV₁ AUC_{0-12h} is estimated to be 250 mL. With a 2-sided test at a 5% significance level and 500 vs. 300 evaluable patients in the two groups, there will be an 90% power to detect a true difference of 59 mL between the treatments. If the withdrawal rate at 24 weeks exceeds 25% overall, additional patients may be randomized to the study to compensate for the loss of data.

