9.4.4 Missing Data

All data collected after treatment withdrawal will be used in the analyses. Patients withdrawn from study will perform an End-of-Study visit after decision to withdraw the patient has been made. Data collected at such visits will be used for analysis even if outside the visit window for the endpoint. Remaining missing data will primarily be imputed using multiple imputation based on baseline characteristics and data collected at post-randomization visits. In addition, a worst-case scenario using the average change in the opposite treatment group will be used for imputation as a sensitivity analysis. For the responder analysis of SGRQ, patients with no available data for imputation will be considered non-responders as a sensitivity analysis. In exacerbation analyses, patients are included with data collected up to last day in the treatment period/period of recording following treatment withdrawal.

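### Under SAP 6.4, early-termination spirometry by Day 53 has no slot for three gated FEV1 endpoints once Week 6 is filled, contrary to the protocol

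*SAP*

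**What the plan says.** SAP 6.4 has two rules for spirometry from patients who leave the study.

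- For AUC0-12h, evening trough and AUC6-12h there is no window: "data collected at visits with 12 hour spirometries will be included in the analysis regardless of the timepoint it was generated".
- For other spirometry, the end-of-study visit is placed by study day: Week 6 up to Day 53, Week 12 from Day 54 to Day 95, Week 24 from Day 96 to Day 179. A restriction follows: "The EOS visit can only be windowed to a visit that is missing or has a missing result".

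SAP 6.3 says: "Early termination data will be mapped to the next available visit number for by-visit summaries". That sentence refers on to 6.4 for the detail.

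Protocol 9.4.4 says of visits made by patients withdrawn from the study: "Data collected at such visits will be used for analysis even if outside the visit window for the endpoint". Protocol 9.4.1, in the paragraph on key secondary endpoints, says that early-termination data enter the analyses. SAP 7.3 says the same of end-of-study visits in the mITT analyses. SAP 3.3, the list of changes from the protocol, does not mention the empty-slot restriction.

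**The concern.** Protocol 7.3.1.1 and SAP 16.1.1.1 show that a patient leaving without Week 12 spirometry is asked for one full session: pre-dose, then serial tests to 12 hours. That session yields AUC0-12h, peak FEV1, AUC0-4h and morning trough together. Under 6.4 the first can count as Week 12 while the other three have nowhere to go.

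Those three are alpha-controlled endpoints in SAP 7.4. Which patients have an observed Week 12 value in a confirmatory test should be settled in the text, not by a programmer choosing between 6.4 as written and the protocol's rule. Discarding a valid post-withdrawal measurement also sits badly with the treatment policy strategy in SAP 2.5.

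**Working it through.** **The plan's own figure.** Protocol 9.2 gives "With a 2-sided test at a 5% significance level", an SD that "is estimated to be 250 mL", and "500 vs. 300 evaluable patients in the two groups", and states that "there will be an 90% power to detect a true difference of 59 mL between the treatments". SE = 250 × √(1/500 + 1/300) = 18.26 mL. Then 59/18.26 = 3.23, and power = Φ(3.23 − 1.96) = 0.898. The stated 90% is reproduced. The placement rule does not change it.

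**Where one 12-hour ET session goes when Week 12 was not done (SAP 6.4)**

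| ET day and visit status | AUC0-12h | Peak FEV1, AUC0-4h, morning trough |
|---|---|---|
| Days 2–53, Week 6 empty | Week 12 | Week 6 |
| By Day 53, Week 6 filled | Week 12 | no slot, unused |
| Days 54–95 | Week 12 | Week 12 |
| Days 96–179 | Week 12 | Week 24 |

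In row 2, Protocol 9.4.1 and 9.4.4 and SAP 7.3 all say the data are used, and 6.4 does not use them. Row 3 is consistent. In row 1 the endpoints are labelled differently, but the Week 6 value enters the imputation of Week 12, because SAP 16.2.2.1 puts all scheduled visits in the model. Row 4 splits the session between two visits.

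**Size of row 2.** The Week 6 target is Day 6 × 7 + 1 = 43. With the ±10-day window it runs from Day 33 to Day 53. The documents give no withdrawal timing, so the following are assumptions: 800 patients, a fraction w withdrawn by Day 168, and every such patient giving an ET session.

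- Constant hazard: S(t) = (1 − w)^(t/168). Unused = 800 × [S(43) − S(53)] if Week 6 was on Day 43.
- Uniform withdrawal: unused = 800 × w × 10/168.
- If every Week 6 visit fell on Day 33, replace S(43) by S(33), and 10 by 20.

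| w | Day 43, constant hazard | Day 43, uniform | Day 33, constant hazard | Day 33, uniform |
|---|---|---|---|---|
| 25% | 12.6 | 11.9 | 25.5 | 23.8 |
| 15% | 7.4 | 7.1 | 14.9 | 14.3 |
| 5% | 2.4 | 2.4 | 4.8 | 4.8 |

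For w = 25% and Day 43: 800 × (0.75^(43/168) − 0.75^(53/168)) = 800 × (0.9290 − 0.9132) = 12.6, or 12.6/800 = 1.6% of patients. The Day 33 columns are an extreme, since they put every Week 6 visit on its earliest in-window day.

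**The case against.** The different treatment of the primary endpoint has a reason. Twelve-hour spirometry is scheduled only at Week 12, so AUC0-12h has no other post-baseline visit to occupy. Peak FEV1, AUC0-4h and morning trough are measured repeatedly, and Protocol 9.4.1 itself draws that contrast. The primary rule agrees with the protocol. This stands: the primary endpoint is not at fault.

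A reader might infer that SAP 6.3, SAP 6.4 and Protocol 9.4.4 are three rival rules throughout. They are not. SAP 6.3 covers by-visit summaries and defers to 6.4, and the 6.4 windows mostly act as next-visit mapping. The wording of 6.3 and 6.4 diverges only in the filled-slot case, where the next available visit, read literally, would be Week 12.

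A reader might also count every ET by Day 53 as lost. At 25% withdrawal and constant hazard that is 800 × (1 − 0.75^(53/168)) = 69 patients. Most of these have an empty Week 6 slot, and their values inform the Week 12 imputation, which arguably meets the protocol's requirement that they be used. This answer does not cover a filled slot, nor the SAP 16.2.4 sensitivity analysis whose imputation model has only baseline and Week 12.

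Existing checks help in part. The average-imputation analysis (SAP 16.1.2, extended by 16.2.2.4) draws on early-termination visits with no day window stated, so it may use values that the main analysis drops. A sensitivity analysis does not repair the main rule. Finally, in the Day 43 scenario each affected patient has an observed Week 6 value at most 10 days earlier in the model, so little information is lost.

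**Conclusion.** Wrong as written, but narrow. For ET by Day 53 with Week 6 already filled, SAP 6.4 leaves peak FEV1, AUC0-4h and morning trough unused, against Protocol 9.4.1 and 9.4.4 and SAP 7.3, without an entry in SAP 3.3. Evening trough is not affected, because it follows the unwindowed rule.

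With constant hazard, Week 6 on Day 43 and full ET attendance, about 13 of 800 patients are affected at 25% withdrawal and about 7 at 15%. The 25% is the trigger in Protocol 9.2 and SAP 4.2 for adding patients, not a forecast. Real attendance would be lower: Protocol 7.3.1.1 makes ET spirometry optional for patients already off study medication, and exempts those who withdraw consent and some safety withdrawals. Earlier Week 6 visits would raise the count, as the working shows. No bias or change in the treatment estimate has been demonstrated.

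ET after Day 95 with Week 12 missed is a related gap that the SAP should address; its size was not estimated. The documents do not support the stronger step of forcing every ET value to Week 12. For repeatedly measured endpoints that is a trade-off, because very early values would replace an imputation that already uses them.

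**What to change.** In SAP 6.4:

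1. State that when the visit in the study-day window is already filled, ET spirometry is assigned to the next missing scheduled visit. For ET by Day 53 with Week 6 done, that is Week 12.
2. State how peak FEV1, AUC0-4h and morning trough are placed when ET falls after Day 95 and Week 12 was missed.
3. Keep the current day-window version as a sensitivity analysis.
4. List in SAP 3.3 any remaining departure from Protocol 9.4.4.

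The cost is a few sentences and a small derivation change. The downside is that a few values from about Days 34–53 would count as Week 12, if Week 6 is attended no earlier than Day 33. The plan already accepts this for the primary endpoint, and the sensitivity analysis would show whether it matters.
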